6.3. SAFETY ANALYSIS SET

The safety (SAF) analysis set will contain all patients who were enrolled and received at least one dose of any study drug.

Document: T:\sas\Debiopharm\Debio_1143\CZA60507\Biostatistics\Documentation\SAP\SAP Text\V5

Author: XXXXXXXXXX Version Number: 5.0
Version Date: 19APR2022

Template No.: CS_TP_BS016 Revision 5
Effective Date: 01Apr2018

Reference: CS_WI_BS005

6.4. INTENTION-TO-TREAT ANALYSIS SET

The intention-to-treat (ITT) analysis set will contain all enrolled patients who took at least one dose of any study drug.

6.5. EFFICACY ANALYSIS SET (PART B ONLY)

The efficacy (EFF) analysis set will contain all ITT patients who have:

- measurable disease according to RECIST v1.1 and/or GCIG criteria (Cohort 4, if applicable),
and
- a baseline tumor assessment and at least one evaluable post-baseline tumor assessment, either CT or MRI for RECIST evaluable patients, or CA-125 dosage performed after baseline, if applicable,
or
- treatment discontinuation occurred before any efficacy assessment was done due to treatment failure, defined as any: death, unacceptable toxicity, clinical deterioration and/or symptoms worsening, except those linked to COVID-19 (COVID-19 recorded as an AE in eCRF).

In order to assess these criteria, prior to each scheduled analysis where efficacy will be monitored, the study's statistician will present each of the below 7 category's data to the Debiopharm's Medical Director and IQVIA's Medical Monitor who will be tasked to adjudicate cases for exclusion from the efficacy population.

Category 1: Patients who did not have a baseline tumour assessment

- a. based on imaging or
- b. CA125 (where appropriate)

Category 2: Patients who did not have measurable disease according to

- a. RECIST or
- b. GCIC criteria (where applicable)

Category 3: Patients who did not have at least 1 post-baseline tumour assessment according to

- a. RECIST or
- b. GCIC criteria (where applicable)

Document: T:\sas\Debiopharm\Debio_1143\CZA60507\Biostatistics\Documentation\SAP\SAP Text\V5

Author: XXXXXXXXXX Version Number: 5.0
Version Date: 19APR2022

Template No.: CS_TP_BS016 Revision 5
Effective Date: 01Apr2018

Reference: CS_WI_BS005

If any of the above listed protocol deviations have been observed in categories 1 to 3, patients will be excluded from the efficacy population and will need to be “replaced”.

Category 4: Patients who discontinued study treatment before the first post-baseline tumour assessment was performed due to treatment failure, except those linked to COVID-19 (COVID-19 recorded as an Adverse Event in eCRF), which include any of the following

- a. Death
- b. Unacceptable toxicity
- c. Clinical deterioration and
- d. Symptomatic worsening

Patients who failed treatment and included in category 4, will be kept in the efficacy population and will not be replaced

Category 5: Any critical deviations that may affect the risk benefit ratio

- a. Cancer diagnosis (inclusion criteria 3 and 11)
- b. Other malignancies (exclusion criterion 13)
- c. Prior anti-cancer treatment (inclusion criteria 4, 5 and 6; exclusion criteria 2, 5, 6 and 7)
- d. Co-morbidities (exclusion criteria 4 and 10)
- e. Inadequate hematologic, renal and hepatic function (inclusion criterion 9)

Category 6: Patients who used any of listed drugs prohibited on this protocol

Category 7: Patients whose treatment had to be delayed or interrupted for reasons related to COVID-19 pandemic only and did not receive at least 25% of the planned Debio1143 dose or didn't receive any dose of nivolumab infusion during cycle 1. Exposure during the first 3 treatment cycles will also be considered as part of the

Document: T:\sas\Debiopharm\Debio_1143\CZA60507\Biostatistics\Documentation\SAP\SAP Text\V5

Author: ██████████

Version Number:

5.0

Version Date:

19APR2022

Template No.: CS_TP_BS016 Revision 5

Reference: CS_WI_BS005

Effective Date: 01Apr2018

Copyright © 2009, 2010, 2012, 2016, 2018 IQVIA. All rights reserved. The contents of this document are confidential and proprietary to IQVIA Holdings Inc. and its subsidiaries. Unauthorized use, disclosure or reproduction is strictly prohibited.

assessment of patients who fall into this category.

Efficacy data assessed after any of these deviations have been observed in patients who are included in categories 5 through 7 will be excluded from the efficacy analysis. However, for category 6 and 7, this will not automatically lead to the exclusion of these patients from the efficacy population (any patient with one of the deviation described in category 5 will be automatically excluded from Efficacy population because these deviations are related to inclusion/exclusion criteria).

In case after the exclusion of efficacy data assessed after protocol violations described in categories 5 and 6 the patients will fulfil the criteria from category 1 or 3, the patients will be excluded from the efficacy analysis set.

Efficacy analysis set is not applicable for part A because TLFs will not be produced based on this analysis set for part A. For part B, in case no patient is excluded from efficacy analysis set (i.e. efficacy analysis set is equal to ITT analysis set), outputs on efficacy analysis set will not be produced.

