#### Part B

Patients will be evaluable for efficacy if the following two conditions are met:

- Measurable disease at baseline as per RECIST v1.1 and/or GCIG criteria (Cohort 4, if applicable),
- At least one efficacy assessment, either computed tomography (CT) or magnetic resonance imaging (MRI) for RECIST evaluable patients, or CA-125 dosage performed after baseline, if applicable, or treatment discontinuation occurred before the efficacy assessment was done due to treatment failure, defined as any of the following: death, unacceptable toxicity, clinical deterioration and/or symptoms worsening.

Non-evaluable patients will be replaced.

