#### **11.5.4. Efficacy population**

The efficacy population is defined as patients who have:

- measurable disease according to RECIST v1.1 and/or GCIG criteria (Cohort 4, if applicable) and
- a baseline tumor assessment and at least one post-baseline tumor assessment, either CT or MRI for RECIST evaluable patients, or CA-125 dosage performed after baseline, if applicable, or
- treatment discontinuation occurred before the efficacy assessment was done due to treatment failure, defined as: death, unacceptable toxicity, clinical deterioration and/or symptoms worsening

Patients with treatment failure will not be replaced and will be included in the efficacy population.

In case of non-permitted concomitant treatments or critical protocol violations that may affect the patient benefit/risk balance (i.e., non-eligibility criteria), efficacy data assessed after such protocol violations will be excluded from the efficacy analysis, as appropriate, but the patient will be kept in the efficacy population. This will be described in detail in the statistical analysis plan (SAP).

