The total sample size will be between 32 (if all cohorts are futile) and 60 evaluable patients (if none of the 4 cohorts is futile). If a patient is not evaluable (i.e. not included in efficacy analysis set) he/she will be replaced.

In Part B, patients will receive Debio 1143 at the RP2D established in Part A, in combination with nivolumab at the standard dose. Per-patient dose adjustments of Debio 1143 will be considered according to the severity of any eventual observed toxicity.

Participants are planned to be treated with Debio 1143 and nivolumab for up to 52 weeks (i.e., 13 cycles, until any of the following events occurs: symptomatic progressive disease (PD), asymptomatic but confirmed PD (as per iRECIST), unacceptable toxicity (per Investigator judgment and despite up to two dose adjustments), patient withdrawal, or treatment delay greater than 4 and 8 weeks (+1 week tolerance) for Debio 1143 and nivolumab, respectively.

Permission to prolong the study treatment for one additional year can be exceptionally granted by the Sponsor, if patients are deriving continuous clinical benefit from the study treatment. Medical justification for extending the treatment and the assessment of the risk/benefit balance must be provided by the Study Investigator and will be discussed with the Sponsor. The decision to further extend study treatment will be re-evaluated on a yearly basis for each patient.

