17.1.3. PRIMARY ANALYSIS OF PRIMARY EFFICACY VARIABLE

Due to the exploratory nature of the trial, there will be no formal hypotheses testing. The primary efficacy analysis will be performed for the EFF analysis set.

At the final analysis for part B, a homogeneity Fisher exact test with a significance level of 0.3 will be conducted in the non-futile cohorts showing a confirmed response rate of at least 15% (≥ 4 responders). If the primary endpoint homogeneity assumption is confirmed, the estimated confirmed ORR will be reported overall and by cohort based on the posterior beta distribution with a two-sided 95% credibility interval. Otherwise, if the homogeneity test does not reach significance level of 0.3, the estimated confirmed ORR and two-sided 95% credibility interval will be similarly reported in each cohort separately.

The efficacy of the futile cohorts and the cohorts with less than 15% confirmed response rate will be reported separately.

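### SAP 6.5 gives two rules for patients whose post-baseline scans are all NE, and the stricter one departs from the protocol without being declared

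*SAP*

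**What the plan says.** Protocol 11.5.4 admits a patient with measurable disease who has "a baseline tumor assessment and at least one post-baseline tumor assessment, either CT or MRI for RECIST evaluable patients", or a CA-125 measurement where that applies, or who stopped for treatment failure before being assessed. Protocol 6.3, which governs replacement, sets the same bar: "At least one efficacy assessment, either computed tomography (CT) or magnetic resonance imaging (MRI) for RECIST evaluable patients".

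SAP 6.5 sets a higher one: "a baseline tumor assessment and at least one evaluable post-baseline tumor assessment". Its alternative route into the set is "treatment discontinuation occurred before any efficacy assessment was done due to treatment failure", with a COVID-19 exception. The section then turns these criteria into seven categories for case review by the sponsor's medical director and the CRO's medical monitor. Categories 1 to 3 trigger exclusion and replacement. Category 3 covers "Patients who did not have at least 1 post-baseline tumour assessment according to" RECIST or GCIG, and there the word *evaluable* is absent.

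The set matters because of two further statements. SAP 17.1.3: "The primary efficacy analysis will be performed for the EFF analysis set". SAP 4.1.2: "If a patient is not evaluable (i.e. not included in efficacy analysis set) he/she will be replaced".

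SAP 4.3 lists the efficacy-set changes from the protocol: the COVID-19 exception and category 7. It does not list this one. SAP 6.5 does not define *evaluable*. The nearest guide is SAP 17.2.1.6, which treats an adequate tumour assessment as one that does not show NE.

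**The concern.** Call a patient NE-only if every post-baseline response is NE, for example because the target lesions were never all evaluated (protocol Appendix C). If *evaluable* means not NE, an NE-only patient fails the assessment route. If that patient then deteriorates and stops, the treatment-failure route is closed too, because an assessment has already been done.

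A patient who fails treatment before any scan is handled the opposite way. Category 4 keeps that patient, and SAP 17.1.2 assigns a confirmed best response of NE, so the patient sits in the denominator as a non-responder. Neither patient has a usable response, yet one counts and the other is dropped and replaced.

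An NE-only patient cannot be a responder. Compared with an ORR that counts NE as non-response, leaving such patients out can only raise the estimate. It also changes who makes up the 8, 11 and 15 patients on whom the cohort decisions rest.

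**Working it through.** **Inputs.** Prior Beta(0.5, 0.5); futility reference 0.05 with threshold 0.2; efficacy reference 0.15 for confirmed ORR with threshold 0.8; looks at 8 and 11, final at 15 (SAP 5.3). Protocol Table 11-1 prints 0.17 as the confirmed reference, so both values are checked. The NE share q is in neither document and is assumed to be 0 to 20%.

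**The plan's boundaries reproduce.** The posterior is Beta(0.5 + r, 0.5 + n − r).
- P(θ ≤ 0.05): 0/8 = 0.643 and 1/11 = 0.224, both above 0.2 (stop). 1/8 = 0.149 and 2/11 = 0.042 (continue).
- P(θ > 0.15): 3/15 = 0.726, 4/15 = 0.892. With 0.17 instead: 0.647 and 0.843. Four responses is the boundary either way.

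**Effect on the rate and the efficacy claim.** Let p be the true ORR among all treated patients, with NE-only patients as non-responders. Dropping a share q gives an efficacy-set rate p′ = p/(1 − q). The chance of claiming efficacy is the sum, over x ≥ 1 responses in 8 and y in the next 3 with x + y ≥ 2, of Bin(x; 8, p′) × Bin(y; 3, p′) × P(Z ≥ 4 − x − y), with Z ~ Bin(4, p′). Confirmed and unconfirmed responses are treated as the same. For p = 15%:

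| Assumed NE share q | Rate in efficacy set | Chance of claiming efficacy |
|---|---|---|
| 0% | 0.15/1.00 = 15.0% | 17.1% |
| 5% | 0.15/0.95 = 15.8% | 19.6% |
| 10% | 0.15/0.90 = 16.7% | 22.4% |
| 20% | 0.15/0.80 = 18.8% | 29.6% |

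The row q = 0 is also the result at any q when NE-only patients are kept, because p already counts them as non-responders.

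**Effect at the first look.** With a 5% response rate in each informative patient, the chance of at least one response is:
- 8 informative patients (NE-only patients replaced): 1 − 0.95^8 = 33.7%
- one of the 8 NE-only and kept: 1 − 0.95^7 = 30.2%
- two of the 8 NE-only and kept: 1 − 0.95^6 = 26.5%

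**Effect on a reported estimate.** At final reporting the treated patients are fixed. Suppose 12 were treated, with one responder and one NE-only. Dropping the NE-only patient gives 1/11, posterior mean 1.5/12 = 12.5%. Keeping the patient gives 1/12, posterior mean 1.5/13 = 11.5%.

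**The case against.** **The SAP may never exclude these patients.** *Evaluable* is undefined, and the SAP's own term for not NE is *adequate*, which 6.5 does not use. The operative text is the category list. NE is a RECIST overall response, so an NE-only patient has had an assessment and falls outside category 3. This stands. A reader might infer that the SAP definitely removes and replaces NE-only patients; the documents support only that one sentence does so on its natural reading and another does not.

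**Calling it bias depends on the target.** If NE is unrelated to response, dropping NE-only patients gives an unbiased ORR among assessable patients. The 33.7% is simply what the 0/8 rule implies for eight informative patients. A reader might infer that a cohort gains extra chances at the looks, but the looks stay at 8 and 11. This stands in part. The upward shift is relative to an ORR that counts NE as non-response, which is the convention the SAP applies to treatment failures before any scan.

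**No final decision is shown to change.** One might set 4/15 against 4/16. Under the protocol wording, however, the NE-only patient would fill one of the 15 places, so 4/16 is not the comparator. Even at 4/16, P(θ > 0.15) = 0.867, above 0.80.

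**The effect is visible and limited.** SAP 17.1.4 repeats the primary analysis in the ITT/Safety set, which keeps everyone dosed, and SAP 10.1 tabulates exclusions by reason. All scans must be NE, which may be uncommon. SAP 4.3 already records futility of the Part B cohorts. All of this stands and limits the practical harm. It does not settle which rule defines the primary set.

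**Conclusion.** The inconsistency is real: SAP 6.5 contradicts itself, and its inclusion criterion departs from protocol 6.3 and 11.5.4 without appearing in SAP 4.3. Whether NE-only patients were actually dropped cannot be told from the documents.

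If *evaluable* is read as not NE, and NE counts as non-response, the stricter rule can only raise the primary ORR. The factor is 1/(1 − q): at most 15.0% to 18.8% over the assumed NE share of 0 to 20%. The matching rise in the chance of claiming efficacy, 17.1% to 29.6%, also treats confirmed and unconfirmed responses as the same.

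Since SAP version 5.0 records futility in Part B, a reader should not infer that a cohort was wrongly declared active. What remains is mainly the reported primary ORR and its credibility interval, plus the question of which rule was used at the futility looks. This should be corrected, but it does not undermine the design.

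**What to change.** Delete *evaluable* from the inclusion criterion in SAP 6.5 so that it matches protocol 6.3 and 11.5.4 and category 3. Add one sentence: a patient with at least one post-baseline assessment whose responses are all NE stays in the efficacy set, counts as a non-responder and is not replaced. State which rule was applied at each futility look and whether any patient was replaced for NE-only scans.

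The cost is one word, one sentence and a check of the exclusion listing. The reported ORR may be slightly lower.

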V5.0	19APR2022	██████████	
Section 6 Analysis Set:
 
 - Clarify that efficacy analysis set is a subset of ITT - Clarify that RP2D is not applicable for Part B - Clarify that any patient with one of the deviation described in category 5 will be automatically excluded from Efficacy population - Clarify that category 7 corresponds to patients whose treatment had to be delayed or interrupted for reasons related to COVID-19 pandemic only and did not receive at least 25% of the planned Debio1143 dose or didn't receive any dose of nivolumab infusion during cycle 1 
Section 7.6 Statistical Test:

Document: T:\sas\Debiopharm\Debio_1143\CZA60507\Biostatistics\Documentation\SAP\SAP Text\V5

Author: ██████████

Version Number:

5.0

Version Date:

19APR2022

Template No.: CS_TP_BS016 Revision 5

Effective Date: 01Apr2018

Reference: CS_WI_BS005

			
 - Update the rounding rules for quantitative summaries, to not have irrelevant decimales 
Section 14 Medications
 
 - Update the definition of Concomitant medications 
Section 18.1.15 Most common TEAE
 
 - Clarify that AEs where the overall percentage is $\geq 5\%$ will also be summarized by SOC and PT 
Section 18.5.1 Vital Signs Markedly Abnormal Criteria
 
 - Low and High Markedly Abnormal Criteria updated for Weight 
Section 20 Pharmacodynamics
 
 - Update the definition of On-treatment period 
Typo corrected throughout all the document

--	--	--	----------------------------------------------------------------------------------------------------------------------------------------------------------------------------------------------------------------------------------------------------------------------------------------------------------------------------------------------------------------------------------------------------------------------------------------------------------------------------------------------------------------------------------------------------------------------------------------------------------------------------------------------------------------------------------------------------------------------------------------------------------------------------------------------------------------------------------------------------------

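### SAP 6.5 removes patients with eligibility deviations from the primary ORR set, protocol 11.5.4 keeps them, and SAP 4.3 does not declare the change

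*SAP*

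**What the plan says.** **Protocol.** Section 6.3 (Part B) begins "Patients will be evaluable for efficacy if the following two conditions are met". The two conditions are measurable disease at baseline, and either a post-baseline assessment or earlier discontinuation for treatment failure. Meeting all eligibility criteria is not among them. Section 11.5.4 then deals with prohibited treatments and with critical violations bearing on benefit/risk, which it glosses in brackets as non-eligibility criteria. Efficacy data assessed after such a violation "will be excluded from the efficacy analysis, as appropriate, but the patient will be kept in the efficacy population".

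**SAP.** Section 6.5 sets up seven categories. Category 5 covers critical deviations affecting risk/benefit, and every item under it is an inclusion or exclusion criterion: diagnosis, other malignancies, prior treatment, comorbidities and organ function. The rules that follow are:

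- Efficacy data assessed after the deviation in "patients who are included in categories 5 through 7 will be excluded from the efficacy analysis".
- Beyond that, "any patient with one of the deviation described in category 5 will be automatically excluded from Efficacy population".
- If, once post-violation data are dropped for categories 5 and 6, "the patients will fulfil the criteria from category 1 or 3, the patients will be excluded from the efficacy analysis set".

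On replacement, SAP 6.5 says that for deviations "in categories 1 to 3, patients will be excluded from the efficacy population and will need to be" replaced, and says nothing of the kind for categories 5 to 7. SAP 4.1.2 has a general rule: "If a patient is not evaluable (i.e. not included in efficacy analysis set) he/she will be replaced".

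The efficacy-set entry in SAP 4.3 (changes from protocol) lists only the COVID-19 amendment to treatment failure and the new category 7. The category 5 rule is recorded in the version 5.0 modification history, worded "Clarify that any patient with one of the deviation described in category 5 will be automatically excluded from Efficacy population".

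**The concern.** The two documents give opposite instructions for the same patients, and the affected set carries the primary endpoint. A reader who uses SAP 4.3 to find departures from the protocol will not find this one.

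The exclusion is applied after enrolment, in an open-label single-arm trial, to a small denominator. An eligibility breach normally exists before any post-baseline scan. If such a patient is kept and the later data are dropped, no usable assessment remains. SAP 17.1.1 sends the response derivation to 17.2.1.2, where a patient without post-baseline assessments is scored NE, which is not a response. Handled that way, the patient stays in the denominator as a non-responder; under SAP 6.5 the patient disappears from it. If instead the responses of these patients count, the exclusion removes responders and non-responders alike.

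Neither planned set need give the protocol's denominator. The efficacy set omits category 5, and the ITT repeat in SAP 17.1.4 also restores treated patients from categories 1 to 3.

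**Working it through.** **1. The rules side by side**

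| | Protocol 6.3 and 11.5.4 | SAP 6.5 |
|---|---|---|
| Patient with eligibility breach | kept in efficacy population | automatically excluded (category 5) |
| Efficacy data after the breach | excluded as appropriate | excluded |
| Category 6 patient with no usable scan left | kept | excluded |
| Declared in SAP 4.3 | – | no |

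SAP 6.5 is also inconsistent with itself. It sends all seven categories for adjudication although category 5 is automatic, and it re-tests category 5 patients against categories 1 and 3 when they are already out.

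**2. The plan's own boundaries**

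Inputs from SAP 5.3: prior Beta(0.5, 0.5), efficacy reference 0.15 for confirmed ORR, threshold 0.80, futility reference 0.05, threshold 0.20. The posterior is Beta(0.5 + r, 0.5 + n − r).

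- Efficacy at n = 15: P(θ > 0.15) is 0.726 for r = 3 and 0.892 for r = 4, so the boundary is 4, as stated.
- Futility: P(θ ≤ 0.05) is 0.643 for 0/8, 0.149 for 1/8, 0.224 for 1/11 and 0.042 for 2/11, so the boundaries are 0/8 and ≤1/11, as stated.

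**3. Effect on the reported ORR**

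SAP 17.1.3 reports the posterior estimate; its mean is (r + 0.5)/(n + 1). The number excluded, k = 1, 2 or 3, is an assumption.

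One confirmed response in a cohort of 11, all kept: 1.5/12 = 12.5% (95% CrI 1.0–35.3).

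- Non-responders excluded, not replaced: 1/10 gives 1.5/11 = 13.6%; 1/9 gives 1.5/10 = 15.0%; 1/8 gives 1.5/9 = 16.7%.
- The responder excluded, not replaced: 0/10 gives 0.5/11 = 4.5% (95% CrI 0.0–21.7).
- Excluded patients replaced under the SAP: the SAP set still shows 1/11 = 12.5%. Keeping them as non-responders gives 1.5/13 = 11.5%, 1.5/14 = 10.7% or 1.5/15 = 10.0%.

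No response in 8, all kept: 0.5/9 = 5.6%. With exclusion and no replacement: 0.5/8 = 6.3%, 0.5/7 = 7.1%, 0.5/6 = 8.3%.

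**4. Direction**

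Take 15 patients at a true rate of 15%, of whom k are category 5 patients responding at rate q. The expected ORR with them kept is [(15 − k) × 0.15 + k × q]/15. Under the SAP rule it is 15%.

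| q | k = 1 | k = 2 | k = 3 |
|---|---|---|---|
| 0 (scored as non-responders) | 14% | 13% | 12% |
| 0.15 | 15% | 15% | 15% |
| 0.30 (assumed) | 16% | 17% | 18% |

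**5. Sensitivity of the decision rule**

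Without replacement, excluding two non-responders moves 3/15 (0.726) to 3/13 (0.802), past 0.80. Excluding one responder moves 4/15 (0.892) to 3/14 (0.765), below it. At the second futility look, excluding one non-responder turns 1/11 (0.224, stop) into 1/10 (0.199, continue). The efficacy boundary is defined only at n = 15, and with the 0.17 reference printed in protocol Table 11-1 the efficacy crossing needs four exclusions (3/11, 0.824). These cases show sensitivity only.

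**The case against.** - **The protocol sentence may not mean ineligible patients.** The gloss non-eligibility criteria could mean violations other than eligibility, and data assessed after a violation fits on-study events better. But neither protocol 6.3 nor 11.5.4 makes eligibility a condition of the set, and SAP category 5 takes over the protocol's wording and fills it solely with eligibility criteria. The mismatch survives either reading.
- **The protocol defers to the SAP.** Section 11.5.4 leaves detail to the SAP and section 11.6 makes the SAP definitive. That covers detail; retention of the patient is stated outright, and SAP 4.3 exists to record reversals of this kind.
- **The change is visible and partly covered.** SAP 6.5 gives a reason (the deviations concern eligibility), the version history records the rule, exclusions are tabulated by reason (SAP 5.3 and 10.1), and an ITT repeat is planned. All of this stands and limits the harm. The ITT repeat still does not reproduce the protocol's denominator if any treated patient falls in categories 1 to 3.
- **Scoring as a non-responder is an inference.** The protocol drops data only as appropriate, the NE rule sits in the unconfirmed-response section, and SAP 17.1.2 assigns NE only for treatment failure. This is fair, and is why the direction is left open and the scoring should be stated.
- **Replacement is settled by SAP 4.1.2.** That is the natural reading, and it makes the no-replacement figures an upper range. The replacement text in SAP 6.5, limited to categories 1 to 3, leaves doubt.
- **The effect is small and the cohorts are futile.** Shifts of a few points sit inside wide intervals, the 0/8 movement comes only from the prior and a smaller n, and the n = 15 figures have no live application if all cohorts stopped at 8 or 11. This is accepted as to size; it does not remove the contradiction.

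**Conclusion.** The concern holds. For patients with eligibility deviations, SAP 6.5 reverses the retention rule in protocol 11.5.4, the reversal changes the denominator of the primary ORR, and SAP 4.3 does not list it. It should be fixed before the ORR is reported.

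The size depends on counts the documents do not give. With one to three affected non-responders in a cohort of 11 with one response, the posterior mean rises by about 1 to 4 percentage points without replacement, and the gap is 1.0 to 2.5 points with replacement (12.5% against 11.5% to 10.0%). Losing the only responder lowers it by 8 points (12.5% to 4.5%). There is no effect if no patient falls in category 5 or is caught by the category 6 re-test. Because Part B is exploratory and SAP 4.3 already speaks of futile cohorts, the live consequence is the published estimate rather than an efficacy claim.

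On timing, SAP version 4.0 (29 July 2021) added the no-pooling statement that SAP 4.3 attributes to futility, and version 5.0 (19 April 2022) then stated the automatic exclusion. The documents show neither the preceding category 5 text nor any motive, and none is inferred.

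**What to change.** In SAP 6.5:

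1. Delete the automatic category 5 exclusion and the sentence that removes category 5 or 6 patients who then meet category 1 or 3. Keep these patients in the efficacy set, as protocol 11.5.4 states.
2. State whether responses after the violation count. If they do not, say that the patient is scored NE and stays in the denominator.
3. Report the ORR with these patients excluded as a sensitivity analysis, and say whether the data exclusion also applies in the ITT repeat.

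If the sponsor prefers to retain the exclusion, list and justify it in SAP 4.3 as a change from protocol and report the primary ORR both ways.

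In either case, state whether category 5 patients were replaced and which rule was used at each futility look. As a separate tidying point, align the category 7 wording: SAP 4.3 refers to one skipped nivolumab infusion in cycle 1, SAP 6.5 to none received.

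The cost is SAP wording and one extra ORR table, with no new data. The reported ORR may move in either direction or not at all.
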